6.5.10 Blood sampling procedure

Blood samples for analysis will be taken on an empty stomach (8-10 hours after the last meal) from a vein with a disposable sterile syringe, catheter or vacutainer with asepsis/antiseptics. The blood is mixed with the anticoagulant (if required by the procedure for preparing the sample to obtain plasma) and in vitro on the day of blood collection is sent at room temperature to the central laboratory.

Blood volume:

- general blood test (erythrocytes, reticulocytes, hemoglobin, leukocytes and expanded leukocyte formula, platelet counting by the Fonio method- 4 ml;
- biochemical analysis of blood (ALT, AST, creatinine, urea, glucose, total bilirubin
- and its fractions) and determination of IgG levels in serum 10 ml;
- virological screening and antinuclear antibodies 5 ml;
- blood type and Rh factor up to 5 ml;
- Coombs test 4 ml;
- coagulogram 4 ml.

Blood volume by visits:

- at the screening stage 32 ml,
- on the 2nd visit 13 ml,
- on the 3rd visit 9 ml,
- on the 4th visit 9 ml,
- on the 5th visit 9 ml,
- on the 6th visit 23 ml.

1 additional blood sample (20 ml in total) is allowed.

| Bioven | Page 51 |
|----------------------------|--------------------------------|
| Trial Code: 2021-BV-ITP-BP | Version 1.4 from July 03, 2023 |

On other days of visits, blood sampling is provided to perform a general blood test. Each test requires 4 ml of blood. Additional blood sampling for a general blood test is performed one day after the visit, which showed a decrease in platelet count below 30×10^9 /l.

Patients may also have periodic general blood tests and / or biochemical blood tests. The amount of blood required for these tests is determined by the patient's condition and duration of treatment, and will be determined in fact, taking into account the non-harm to the patient.

If the sample was not taken according to the time scheduled by the protocol (missed), the labeled tube remains empty. Information explaining this event is entered into the CRF and primary documentation, and sampling continues at the scheduled time.

6.5.11 Plasma production procedure

In detail, the process is regulated by the Manual of Laboratory Procedures provided by the Central Laboratory selected by the Sponsor.

After sampling, the closed tubes are inverted several times to ensure mixing with the anticoagulant recommended for the study (citrate / EDTA). The presence of visible clots indicates that the study is impossible. In this case, the Sponsor is informed immediately.

The tubes are centrifuged at a temperature of $21 \degree C$ at 2000g for 20 minutes The presence of visible hemolysis indicates the unsuitability of the material. In this case, the Sponsor is informed immediately.

Plasma over the precipitate of blood cells is collected in a plastic tube (0.4-0.5 ml of plasma) over the precipitate is not taken!) And re-centrifuged for 20 min at 2000 g (the last 0.2 ml of plasma after re-centrifugation is not taken). The total plasma yield should be at least 3.8 - 4 ml.

The obtained plasma sample is sent to the central laboratory determined by the Sponsor (temperature regime - in accordance with the manual of laboratory procedures provided by the contracting laboratory).

6.5.12 Procedure for storage and transportation of biological samples

In detail, the process is regulated by the Manual of Laboratory Procedures provided by the Central Laboratory selected by the Sponsor.

Storage of aliquots of blood plasma samples from the moment of their receipt to the beginning of bioanalytical procedures is carried out at a temperature regulated by the manual of laboratory procedures provided by the contracting laboratory. The main samples that do not require freezing after receipt until the moment of transfer to the courier should be stored in a packaged, ready for transfer form at a temperature of 2-8 ° C. Sending such samples to the Bioanalytical Laboratory is carried out in accordance with laboratory guidelines.

Re-thawing / freezing of aliquots of plasma samples is not allowed for samples requiring freezing.

All plasma samples (basic and archival aliquots) are subject to transfer to the Bioanalytical Laboratory).

The main samples must be stored in packaged form after receipt and until transfer to the Bioanalytical Laboratory.

Time of storage of archival aliquots of plasma on a clinical basis before transfer to the Bioanalytical laboratory - no more than the term provided by the laboratory manual.

The transfer of serum samples from the clinical base to the Bioanalytical Laboratory is accompanied by the Direction and the Act of acceptance and transfer of samples of the courier company, determined by the Sponsor. The forms of the above documents are provided by the Sponsor.

| Bioven | Page 52 |
|----------------------------|--------------------------------|
| Trial Code: 2021-BV-ITP-BP | Version 1.4 from July 03, 2023 |

The referral is signed by the Responsible Investigator of the clinical base, or a person authorized by him. The original is transferred to the Bioanalytical Laboratory, a copy remains at the clinical base. The act of acceptance and transfer of samples (in 2 copies) is signed by the Responsible investigator of the clinical base (or his authorized person) and a representative of the courier company, and upon delivery to the Bioanalytical Laboratory - a representative of the courier company and responsible executor of the bioanalytical laboratory.

If necessary, if provided by the laboratory manual, the transport of biosamples to the laboratory is carried out by a specialized courier service. Period of transportation - no more than 8 hours or the term provided by the laboratory manual, in the frozen kind in the cryocontainers filled with "dry ice" (solid carbon dioxide).

Upon full completion of the study and after the period of storage of archival samples agreed with the Sponsor and obtaining the written permission of the Sponsor for their disposal, the remaining unclaimed archival samples of blood plasma are subject to destruction in the Bioanalytical Laboratory. An appropriate act on the destruction of archival samples of blood plasma, which is stored in the archives of the bioanalytical laboratory for at least 15 years.

Serum samples for serological and biochemical tests, as well as whole blood for hematological tests are delivered to the Bioanalytical Laboratory on the day of their receipt by a special courier service at room temperature. The design of the accompanying documentation is similar to that for plasma samples.

Invoices are stored together with the directions and acts of acceptance of the transfer for 15 years in the archives of the research center.

6.5.13 Analysis of deviations from the plan of bioanalytical study

All deviations from the initial statistical processing plan will be described and justified in the relevant sections of the Final Clinical Trials Report. The method of analysis of deviations from the research plan is based on the principles set out in the current instructions.

The withdrawal of subjects from the study will be analyzed against the criteria under this Protocol. Quantitative determination will be performed for all biosamples received for analysis, including biosamples of subjects that dropped out of the study. The results obtained will be included in the Analytical Report.

Re-analysis using archival biosamples, if necessary, should be carried out in all cases of confirmed inability to obtain a reliable result:

- in case of confirming the fact of mixing biosamples;
- in case of confirming the error of the operator/performer during the sample preparation, analytical procedure, and post-analytical period;
- in the absence of sufficient amount of biomateur;
- in case of technical problems with equipment or reagents, conditions of transportation and/or storage of biosamples.

The statistical analysis will not include the results of those subjects for whom the data obtained will not be suitable for analysis. Such data should be excluded from the calculations.

6.5.14 Rules for stopping parts of a clinical trial and (or) a clinical trial in general.

The study may be stopped for the following reasons: 1. Initiated by the Sponsor:

- a. obtaining new toxicological or pharmacological data, or data on SAE related to the study drug, forcing a review of a previous evaluation of the benefits / risks of participating in the study;
- b. the frequency of AEs associated with the study drug and / or their severity do not allow to continue the study;
- c. other reasons, including administrative.
- At the initiative of the investigator: the frequency of AEs associated with the drug and
 / or their severity unacceptably increases the risk of participation of patients in the
 study;
- 3. According to the decision of regulatory authorities.

In case of premature termination of the study, the sponsor should inform the staff of the research centers, as well as regulatory authorities, indicating the reason for the premature termination of the study.

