- Patient's wish
- Occurrence of severe and/or unexpected AE/AR in patient during the study, that require discontinuation of the drug;
- The need to prescribe drugs prohibited in this study.
- Significant deterioration of the patient's condition during the study period;
- Failure of the patient to adhere to the treatment regimen;
- Failure of the patient to follow the procedures established under the protocol;

Due to the variability of PLT levels in patients with chronic immune thrombocytopenia (wave), it is possible to re-screen or extend the duration of the screening phase, but only if the subject meets all other specified inclusion criteria and has no inclusion or exclusion criteria.

Patients who drop out at the screening stage are not included in the efficacy and safety analysis, as they do not receive any doses of the investigational drug (ID).

Patients who do not receive a full course of study drug are included in the safety analysis but not in the efficacy analysis.

Patients who dropped out of the study after completion of SD administration during the followup period are considered in the efficacy and safety analysis. The data of such patients are evaluated by parameters that can be analyzed at a certain point in time. The dropped data are not analyzed.

For all patients who complete the study due to AE, requiring discontinuation of treatment with the studied drugs, it is necessary to conduct the procedures of the final visit in the near future after the development of AE. After stopping treatment, the patient should be monitored until the reaction disappears or its clinically significant signs. Patients who received at least 1 dose of SD but prematurely dropped out of the study are included by the investigator in the analysis of tolerability of the study drug.

The reasons for premature withdrawal from the study are indicated in the Individual registration form.

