scheme is recommended by the EMA and this Protocol, the total number of patients in the group is 82, the effectiveness of the use of IVIG in the treatment of ITP is indicated - 78% [Parodi E, Russo G, Farruggia P, Notarangelo LD, Giraudo MT, Nardi M, et al. Management strategies for newly diagnosed immune thrombocytopenia in Italian AIEOP Centres: do we overtreat? Data from a multicentre, prospective cohort study. Blood Transfus. 2020;18(5):396.]. According to our data and data from the literature, immunoglobulin belongs to drugs with a highly variable efficiency of 20-25%. Therefore, for a non-inferiority study, we consider it appropriate to set δ (the limit of the difference in efficiency between the obtained and expected results) at the level of -25%.

Thus, for a significance level of 5% and a statistical power of 80%, the effectiveness of the drug in the comparison model reaches 78%, the limit of the difference in specific weights (difference in effectiveness) without clinical significance δ is - 0.25. Then the calculation of the minimum sample size will look like this:

 $n = (1,96+1,28)2 \times (0,78 \times (1-0,78) / (0,78 - 0,78 + 0,25)^2 = 29$

Considering the risk of dropping out of patients for various reasons (20%), 36 patients will be included in the study.

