10.3.5. Significance level

The level of significance for the Shapiro-Wilk test is set at 0.01, and for other statistical tests at 0.05. In the case of the effect of multiple comparisons, the adjustment of the level of significance will be applied using the Holm method or the Benjamini-Hochberg method.

10.3.6. Work with missing or incomplete data.

Missing or incomplete data will be replaced using the Last-Observation-Carried-Forward (LOCF) method. Or by the method of enlarging the intervals for series where the transfer of the last measurement is not applicable.

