10.4. Data set for analysis

ITT (Intention-to-treat population) - all study participants who took the study drug at least once. Data from this sample will be used for safety analysis.

PP (Per Protocol) - all patients who met the requirements of the protocol. This population includes all patients who received protocol therapy in full, completed all scheduled visits, and had no significant protocol deviations. The data obtained on this sample will be used for analysis according to the criteria of drug effectiveness.

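### Section 6.5.13 excludes unsuitable results without saying whether the subject or the value goes, and one reading lets patients leave the efficacy denominator

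*Combined protocol and SAP*

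**What the plan says.** Section 6.5.13, which covers deviations from the bioanalytical plan, ends with two sentences. The first takes subjects as its unit: "The statistical analysis will not include the results of those subjects for whom the data obtained will not be suitable for analysis". The second takes data: "Such data should be excluded from the calculations". Neither defines suitability, says who decides, or says when.

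Three other sections govern the same situation:

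- Section 5.3, on patients lost after a full course: "Patients who dropped out of the study after completion of SD administration during the followup period are considered in the efficacy and safety analysis". It adds that they are assessed on whatever parameters can be analysed, and then: "The dropped data are not analyzed".
- Section 10.3.6: "Missing or incomplete data will be replaced using the Last-Observation-Carried-Forward (LOCF) method". Where carrying forward does not apply, intervals are to be enlarged.
- Section 10.4 bases efficacy on the per-protocol (PP) set: "This population includes all patients who received protocol therapy in full, completed all scheduled visits, and had no significant protocol deviations". Safety uses "all study participants who took the study drug at least once".

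The primary endpoint (8.1) is R: a platelet count above 30 x 10⁹/L and at least double baseline, confirmed on two or more tests separated by seven days or more, without bleeding.

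**The concern.** R depends on a laboratory count and on a second, confirming count. If a count proves unusable and R cannot be confirmed from the others, the patient would ordinarily be scored as not R. Under the subject-level reading of 6.5.13, that patient is removed instead. The numerator is unchanged and the denominator shrinks, so the response rate rises.

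Because suitability is undefined and the study is open-label, two statisticians could apply the sentence differently and reach different denominators from the same data. Correcting the population in 10.4 alone would leave this sentence in force.

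**Working it through.** **1. Does the rule reach the primary endpoint?** It can. Section 6.5.6 lists the platelet count among the laboratory tests. Section 6.5.7 covers blood as well as plasma and serum, including haematological analysis. Section 6.5.12 sends whole blood to the same laboratory on the day of sampling. The exclusion sentence is not limited to non-efficacy tests. The re-analysis that 6.5.13 allows for laboratory faults relies on archived samples. The stored aliquots described in 6.2 and 6.5.12 are serum or plasma, so re-analysis may not recover a failed platelet count.

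**2. How do the rules fit together under each reading?**

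| Other rule | 6.5.13 removes the subject | 6.5.13 removes the value |
|---|---|---|
| 5.3, dropouts after full dosing | Conflict: 5.3 keeps the patient | Consistent: 5.3 also leaves the lost data unanalysed |
| 10.4, safety set | Conflict: the set is all treated patients | Consistent |
| 10.3.6, replacement | Nothing is left to replace | Possible sequence (exclude, then replace), but not stated |

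**3. Inputs for the size of the effect.** Reference rate p0 = 0.78, n0 = 82 and the Wald interval come from 10.1 and 10.2; the margin of -0.25 from 10.2 and 10.3.7. Enrolment is 36 in 10.2 and 40 in 4.1.

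The plan's own figure reproduces: n = (1.96 + 1.28)² x 0.78 x 0.22 / 0.25² = 28.82, rounded up to 29. Allowing for 20% dropout, 28.82/0.8 = 36.03, stated as 36.

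**4. Lower limit.** With x responders among n and p = x/n:

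L = p - 0.78 - 1.96 x √[p(1 - p)/n + 0.78 x 0.22/82]

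Non-inferiority is concluded if L > -0.25. The reference variance term is 0.1716/82 = 0.00209.

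Worked case, 25/36: p = 0.6944; p(1 - p)/n = 0.00589; standard error = √0.00799 = 0.0894; L = -0.0856 - 0.1752 = -0.261.

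| Before | L (points) | Removed | After | L (points) |
|---|---|---|---|---|
| 25/36 | -26.1, fail | 1 non-responder | 25/35 | -24.0, pass |
| 24/36 | -29.2, fail | 3 non-responders | 24/33 | -22.9, pass |
| 24/36 | -29.2, fail | 2 non-responders, 1 responder | 23/33 | -26.4, fail |
| 27/40 | -27.6, fail | 2 non-responders | 27/38 | -23.9, pass |
| 20/29 | -28.1, fail | 2 non-responders | 20/27 | -22.7, pass |

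The last row starts from the planned evaluable number, 29, rather than from everyone enrolled. The one-sample criterion also given in 10.1 behaves the same way: 24/36 gives -26.7 (fail) and 24/35 gives -24.8 (pass).

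**The case against.** The case against has several parts, and much of it stands.

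- **Whole-subject deletion.** A reader might infer that 6.5.13 plainly deletes subjects. The documents do not settle this. The second sentence speaks of data, and the section concerns samples. On the value-level reading the rule is close to what one would want, and the clash with 5.3 disappears.
- **Contradiction with 10.3.6.** A reader might infer a direct one. An invalid value can be excluded and then handled as missing. What is lacking is a statement of that order.
- **Missed samples.** These are not governed by 6.5.13. Section 6.5.10 has its own rule: the tube stays empty, the reason is recorded and sampling continues.
- **Timing.** A reader might infer that exclusions would be chosen after results are seen. The text gives no timing, so this is a possibility left open, not a stated practice. Section 6.5.13 does promise that departures from the statistical plan will be described and justified. However, an exclusion made under this sentence follows the plan and is not a departure from it.
- **The larger route.** The PP set in 10.4 already removes non-completers and patients with significant deviations. That is the main problem. But a patient who attended every visit and has one unusable count can be in the PP set and still be removed by 6.5.13.
- **Worst case.** If three of 36 patients were lost independently of response, with 12 non-responders, the chance that all three are non-responders is 220/7140, about 3%. Five post-dose counts are scheduled (48 hours and days 7, 14, 21 and 28), so one lost sample will often leave R assessable. The losses that matter here are not independent of response, though: a patient whose R cannot be confirmed without the lost count is one who would otherwise be scored as not R.

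**Conclusion.** The point holds as an undefined and ambiguous exclusion rule, secondary to the PP definition in 10.4. On the subject-level reading it conflicts with 5.3 and with the all-treated safety set, and it can inflate the response rate. On either reading its relation to 10.3.6 is unstated.

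One to three exclusions can reverse the conclusion, but only if the result lies near the boundary and those excluded are non-responders. With one responder among three exclusions, the 24/36 example still fails. The figures assume the Wald limit of 10.1 with n0 = 82 and p0 = 0.78 taken as given. They show what the rule could do; they do not forecast how often it would. The documents do not support the wider inference that 6.5.13 by itself decides the non-inferiority result.

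**What to change.** Replace the two closing sentences of 6.5.13 with a value-level rule:

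- A laboratory value is declared unanalysable only by written criteria, with a named decision-maker, fixed before database lock. It is then set to missing.
- The subject stays in the efficacy and safety analyses.
- If R cannot be confirmed from the remaining valid counts, the subject is scored as not R.
- Every such value is listed in the report.

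Three other sections must change with it, or the rule creates new contradictions:

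- **10.3.6:** state that carrying a value forward may not be used to confirm R. Otherwise a single qualifying count could serve as its own confirmation.
- **10.4:** amend the efficacy set so that a patient with an unusable or absent count is not removed by the completer condition.
- **5.3:** use the same wording for dropouts after full dosing.

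The cost is text in four sections, with no new visits, samples or patients. The response rate may be slightly lower. With all 36 kept, the two-sample limit needs at least 26 responders (26/36: -22.9; 25/36: -26.1). With 40 it needs at least 28 (28/40: -24.8; 27/40: -27.6).

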6.6 Content of visits

Visit 1 (days -14 ... -1) Screening. Assessment of compliance with inclusion / exclusion (exclusion) criteria based on screening results.

The procedure for taking biomaterial for laboratory analysis is carried out at the collection point (if the researcher thinks the patient is mobile) or the visiting team of the Central Laboratory designated by the Sponsor.

The following procedures will be performed:

- Signing an Informed Consent Form to participate in the study; forms for processing the results of routine examination in a clinical trial;
- Collection and registration of demographic data (sex, age, race);
- Collection of anthropometric data (height, body weight, BMI calculation);
- Collection of medical anamneses (anamnesis of ITP, data on the reception of previous therapy ITP, allergy anamnesis, transfusion anamnesis, comorbidity analysis, data on the treatment of comorbidities, bad habits)
- Physical exploring (necessarily be sure to assess the severity of the hemorrhagic syndrome (exploring of the skin and mucous membranes, the presence of bleeding); palpation and percussion of the abdominal organs; auscultation and percussion of the heart and lungs.
- Measurement of vital signs (body temperature, heart rate, blood pressure, respiratory rate);
- Electrocardiography in 12 deviations;
- General blood test: hemoglobin, hematocrit, erythrocytes, reticulocytes (at the lowered level of hemoglobin, but not below 90 g/L), leukocytes + expanded leukocyte formula, platelet count according to Fonio;
- Biochemical blood test: ALT, AST, bilirubin, creatinine, urea, glucose;
- · Analysis for HIV, RW, HBsAg, anti-HCV, CMV, EBV or data from primary documentation;
- Determination of the level of total IgG in blood serum in grams per liter;
- Blood test for blood type and rhesus factor;
- Coagulogram (PTI, fibrinogen, APTT);
- Blood test for antinuclear antibodies (ANA);
- Straight Coombs' test (antiglobulin test);
- General urine analysis: color, transparency, question. weight; pH, glucose, protein, ketone bodies; sediment microscopy (erythrocytes, leukocytes, cylinders, crystals, bacteria / fungi);
- Pregnancy test for women of reproductive age;

- Assessment of the patient's compliance with the inclusion / non-inclusion criteria based on the screening results;
- Rating according to the exclusion criteria;
- Appointment of the date of hospitalization.

All screening data are entered into the primary documentation and IRF of patients. The researcher checks the patient's compliance with the inclusion/exclusion (exclusion) criteria and decides on possible participation in the clinical trial. Due to the variability in PLT levels in patients with chronic immune thrombocytopenia (wave-like), it is possible to re-screen or extend the duration of the screening stage, but only if the study subject meets all other specified inclusion criteria, does not have non-inclusion and exclusion criteria.

Visit 2. (Day 0, Day +1, Day +2): Study Drug administration within 2 days. Observation.

Content of the visit:

The patient is hospitalized for 3 days for the introduction of the Study Drug (SD).

- 15 minutes before the start of each SD administration and after drug administration, a
 physical exploring is performed: determination of the dynamics of the hemorrhagic
 syndrome (exploring of the skin and mucous membranes, the presence / absence of
 bleeding); palpation and percussion of the abdominal organs; auscultation and percussion of
 the heart and lungs; Measurement of vital signs (body temperature, heart rate, blood pressure,
 respiratory rate);
- Administration of SD for 2 consecutive days at a dose of 0.8-1.0 g/kg per day (course dose 1.6-2.0 g/kg);
- After 48 hours (+/- 2 hours) from the beginning of the first SD administration, a blood sample is taken for general blood test, biochemical blood test, Coombs' test and Ig G level according to the "Schedule of Procedures";
- AE/AR registration;
- Discharge of the patient and appointment of the date of the next visit.

Visit 3 (Day +7 ± 1 day): Observations.

The patient is:

- Physical exploring is performed: determination of the dynamics of the hemorrhagic syndrome (exploring of the skin and mucous membranes, the presence / absence of bleeding); palpation and percussion of the abdominal organs; auscultation and percussion of the heart and lungs;
- Measurement of vital signs (body temperature, heart rate, blood pressure, respiratory rate);
- General blood test: hemoglobin, hematocrit, erythrocytes, leukocytes, platelet count according to Fonio;
- Coombs' test is performed in case of hemolysis according to the laboratory test at the previous visit;
- Determination of total IgG in serum (g/l);
- Rating according to the exclusion criteria;
- AE/AR registration;
- Discharge of the patient and appointment of the date of the next visit.

Visit 4 (Day 14 ± 2 days): Observations.

| Bioven | |
|----------------------------|--|
| Trial Code: 2021-BV-ITP-BP | |

The visit may be conducted by telephone / video, provided that an adequate assessment of the patient's condition is possible and that a laboratory examination is mandatory at the collection point of the Central Laboratory designated by the Sponsor.

At visit 4, the following procedures are performed:

- Physical exploring is performed: determination of the dynamics of the hemorrhagic syndrome (exploring of the skin and mucous membranes, the presence / absence of bleeding); palpation and percussion of the abdominal organs; auscultation and percussion of the heart and lungs;
- Measurement of vital signs (body temperature, heart rate, blood pressure, respiratory rate);
- General blood test: hemoglobin, hematocrit, erythrocytes, leukocytes, platelet count according to Fonio;
- Coombs' test is performed in case of hemolysis according to the laboratory test at the previous visit;
- Determination of total IgG in serum (g/l);
- Rating according to the exclusion criteria;
- AE/AR registration;
- Discharge of the patient and appointment of the date of the next visit.

Visit 5 (Day 21 ± 3 days): Observations.

The visit may be conducted by telephone / video, provided that an adequate assessment of the patient's condition is possible and that a laboratory examination is mandatory at the collection point of the Central Laboratory designated by the Sponsor.

- At visit 4, the following procedures are performed:
- Physical exploring is performed: determination of the dynamics of the hemorrhagic syndrome (exploring of the skin and mucous membranes, the presence / absence of bleeding); palpation and percussion of the abdominal organs; auscultation and percussion of the heart and lungs;
- Measurement of vital signs (body temperature, heart rate, blood pressure, respiratory rate);
- General blood test: hemoglobin, hematocrit, erythrocytes, leukocytes, platelet count according to Fonio;
- Coombs' test is performed in case of hemolysis according to the laboratory test at the previous visit;
- Determination of total IgG in serum (g/l);
- Rating according to the exclusion criteria;
- AE/AR registration;
- Discharge of the patient and appointment of the date of the next visit.

Visit 6 (Day 28 ± 1 - 3 days): Observations.

Face-to-face visit.

At visit 6, the following procedures are performed:

- Physical exploring is performed: determination of the dynamics of the hemorrhagic syndrome (exploring of the skin and mucous membranes, the presence / absence of bleeding); palpation and percussion of the abdominal organs; auscultation and percussion of the heart and lungs;
- Measurement of vital signs (body temperature, heart rate, blood pressure, respiratory rate);
- General blood test: hemoglobin, hematocrit, erythrocytes, leukocytes, platelet count according to Fonio;
- Biochemical blood test: ALT, AST, bilirubin, creatinine, urea, glucose, Coombs' test;
- Determination of total IgG in serum (g/l);

• Rating according to the exclusion criteria;

- AE/AR registration;
- Final visit.

